Effect of T6 Dermatome Electrical Stimulation on Gastrooduodenal Motility in Healthy Volunteers

NCT03316105

5/15/2017

Title of the Study:	Effect of T6 Dermatome Electrical Stimulation on Gastroduodenal Motility in Healthy Volunteers
Protocol Version:	2.0 (dated 5/15/2017)
Principal Investigator:	[name].
Fellow Co-investigator(s):	[name]., R.D., [name].
Technician coordinators:	[name], B.S.; [name], M.H.A.; [name] ; [name] BSN; [name]
Statistician:	[name].

Abstract

Background

Previous studies demonstrated that electrical stimulation in the upper abdomen inhibited postprandial antral motility, possibly through activation of somatovisceral stimulation or central mechanisms. Percutaneous electrical neurostimulation of dermatome T6 was associated with appetite reduction and, along with a proper diet, achieved a significantly greater weight reduction than diet alone in morbidly obese subjects. The effect on appetite and weight could be related to an effect on gastric motor functions. However, the effects of T6 dermatomal electrical stimulation on gastric motor functions are unclear.

Hypothesis

T6 dermatomal electrical stimulation treatment results in inhibition of postprandial antral motility in healthy volunteers.

Aim

We aim to compare measurements of postprandial antral motor activity in healthy participants treated with sham versus active T6 dermatomal electrical stimulation (delivered by a TENS unit).

Methods

We shall perform multilumen gastroduodenal manometry to measure postprandial antral motor activity in response to sham versus active T6 dermatomal electrical stimulation in a parallel group study design.

Significance

This study will form the foundation for the potential subsequent application of dermatome electrical stimulation for altering gastroduodenal motility.

Research Plan

[figure not shown]
BACKGROUND

A surgically implantable gastric stimulator (gastric pacemaker) has been used to treat obesity; this achieves excess weight loss up to 40% in approximately 1 year (1). The modulation of neuronal activities and release of certain hormones with an implantable gastric stimulator may explain the reduction of appetite and the increase of satiety, such as a decrease in ghrelin levels (2).

Viscerovisceral spinal reflexes that are thought to be relayed through sympathetic pathways appear to play an important role in the autonomic control of thoracoabdominal viscera, such as the heart and great vessels (3). However, somatic stimulation may also affect visceral function through autonomic reflexes. The best known somatovisceral response is the effect of cold pain on vasomotor reactions (4). Evidence suggests that the gastrointestinal tract may also be influenced by such somatovisceral reflexes; thus, in anesthetized rats, cutaneous stimuli applied to the abdomen and hind paw decrease and increase stomach motility, respectively. Whereas the latter reflex response appears to relay centrally and the efferent limb of the reflex is located in vagal fibers, the response to abdominal stimulation involves a somatosympathetic reflex that relays at the level of the spinal cord, being retained in cervical cord-transsected rats (5).

[figure not shown]
In studies performed by the Principal Investigator 30 years ago (6), sustained somatic stimulation by transcutaneous electrical nerve stimulation (TENS) was applied to the skin of human volunteers while simultaneously monitoring their upper gastrointestinal phasic pressure activity, extraintestinal vasomotor indices, and plasma levels of putative humoral mediators of autonomic reflexes (Figure 1).

Figure 1.

Stimuli were applied either to the hand (C8-T1) or to the upper abdomen (T5-T10) to determine whether impulses at these two dermatomes produced different effects on fed antral phasic pressure activity. TENS resulted in significant reduction ($p=0.007$) in antral motility index when applied to the hand and abdomen, as compared with sham stimulation (Figure 2). This was associated with increases in skin conductance (suggesting vasomotor changes) and plasma beta-endorphin levels (suggesting a central stress pathway was stimulated), but there were no changes in pulse, blood pressure, or circulating catecholamine levels. No qualitative changes in proximal intestinal pressure activity were detected. These studies suggested that sustained somatic stimuli resulted in reduced postprandial antral phasic pressure activity and the similarity in the responses to TENS applied to the hand and abdominal dermatomes suggests that the somatovisceral responses may relay at the central level. It is assumed that such a central effect results in inhibition of firing of vagal cholinergic pathways that are typically stimulated in the post-prandial period by the presence of food in the stomach activating vagal afferents.

Figure 2.

Electrical stimulation of the dorsal columns of the spinal cord to prevent the perception of intractable neuropathic pain signals in two patients was associated with appetite reduction and weight loss (7). In a large study, Ruiz-Tovar et al. showed that percutaneous electrical neurostimulation of dermatome T6 was associated with appetite reduction and, along with a proper diet, achieved a significantly greater weight reduction than diet alone in morbidly obese patients (8). The mechanism of appetite reduction in response to treatment is unknown, but could be explained by a possible effect on gastric motor functions.

The effects of T6 dermatomal electrical stimulation on gastric motor functions, particularly gastroduodenal motility, are unclear.

HYPOTHESIS AND SPECIFIC AIM

Hypothesis

T6 dermatomal electrical stimulation treatment results in inhibition of postprandial antral motility in healthy volunteers.

Aim

We aim to compare measurements of postprandial antral motor activity in 16 healthy participants treated with sham versus active T6 dermatomal electrical stimulation (delivered by a TENS unit).

EXPERIMENTAL DESIGN

Healthy volunteers will be recruited for this one-day study that will take place in our gastric functions laboratory at the Clinical Research Trials Unit (CRTU) at Mayo Clinic. Participants will have a multilumen gastroduodenal manometry tube placed transnasally after overnight fasting.

In a parallel group design, all 16 participants will receive a standardized breakfast meal to assess baseline post-prandial gastric motility followed by ingestion of the same standardized meal as lunch (500 kcal, see Appendix 1) at 4 hours after the ingestion of the first (breakfast) meal. Prior to the lunch meal, the subjects will receive either sham or active T6 Dermatome cutaneous stimulations with a wireless TENS unit applied 15 minutes before ingestion of the lunch meal, and immediately after completing ingestion of this meal for a duration of 60 minutes.

Participants will be randomized to either sham or active treatment at the lunch meal. Hence, 8 participants will receive one set of sham stimulations (pre and post prandial in relation to lunch time meal) and 8 participants will receive one set of active stimulations (pre and post prandial in relation to lunch time meal). Participants randomized to sham will have a TENS unit connected without activation of the electrodes.

Gastroduodenal manometry will be performed to assess gastroduodenal motility during the postprandial phase of each meal, with the primary measurement being the antral motility index during the first postprandial hour.

METHODS

Participants

At least 16 healthy volunteers will be recruited for the study. We may screen up to 24 participants in order to ensure 16 fulfill eligibility criteria and complete the study. Additional participants from our list of eligible candidates will be recruited to replace early withdrawals, in the event that participants withdraw on testing day before having completed all investigative testing. Participants will be randomized in blocks of four.

Inclusion Criteria

- a. Healthy volunteers with $BMI \leq 34.99 \text{ kg/m}^2$ residing within 125 miles of Mayo Clinic in Rochester, MN; these will be healthy individuals with no unstable psychiatric disease and not currently on treatment for cardiac, pulmonary, gastrointestinal, hepatic, renal, hematological, neurological, or endocrine (other than hyperglycemia on diet) disorders.
- b. Age: 18-65 years.
- c. Gender: Men or women. Women of childbearing potential will be using an effective form of contraception, and have negative pregnancy tests within 48 hours of the test day.
- d. Subjects must have the ability to provide informed consent before any trial-related activities.

Eligible individuals will be asked to avoid taking additional medications and supplements for one week before and after the test day, unless reviewed and approved by the study team.

Exclusion Criteria

- a. Abdominal surgery other than appendectomy, Caesarian section or tubal ligation.
- b. Positive history of chronic gastrointestinal diseases, systemic disease that could affect gastrointestinal motility, or use of medications that may alter gastrointestinal motility.
- c. Positive history of spinal cord injury and/or chronic back pain.
- d. Significant untreated psychiatric dysfunction based upon screening with the Hospital Anxiety and Depression Inventory (HAD) (9) If such a dysfunction is identified by a HAD score >11 on either Anxiety or Depression or difficulties with substance or eating disorders, the participant will be excluded and given a referral letter to his/her primary care doctor for further appraisal and follow-up.
- e. Intake of medication, whether prescribed or over the counter (except multivitamins), within 7 days of the study. Exceptions are birth control pill, estrogen replacement therapy, thyroxine replacement therapy, low dose analgesia or anti-inflammatory medications (Acetaminophen and Ibuprofen) and any medication administered for co-morbidities as long as they do not alter gastrointestinal motility.
- f. Subjects may also be excluded from participation for other factors at the discretion of the principal investigator.

T6 Dermatomal Stimulation

T6 dermatomal stimulation will be achieved by utilizing an Elira TENS device (Elira Therapeutics, Inc., St. Louis, MO), following the company's device protocol. The Elira device provides a broad range of options for stimulation parameters. In particular, pulse width is programmable from 25 μ sec to 400 μ sec, pulse amplitude from 1 mA to 45 mA, pulse frequency from 1 Hz to 200 Hz, session duration from 5 min to 60 min, and number of sessions per day from 0 to 8 sessions.

(external diameter: 6mm) that is introduced along a guidewire placed with aid of fluoroscopy. Each of the fifteen perfusion channels of the manometric tube will be perfused with distilled water via a pneumohydraulic pump (perfusion rate: 0.15ml/min, perfusion pressure: 14psi) and attached to a strain gauge transducer (model PX-MK099, Edwards Lifesciences, Irvine, CA.). One side opening was made in each channel of the multi-lumen tube, and the positions of these openings were at the tip of the tube will be fluoroscopically placed across the antroduodenal region; thus, the tip of the tube lies near the ligament of Treitz. Fasting pressure activity will be recorded in each volunteer for 1 hour while they are fasting. Then, each individual will ingest a 500 Kcal mixed solid-liquid meal consisting of scrambled egg, bread, pudding, and milk at each test meal (Appendix 1). Pressure activity will be recorded after each test meal (10). The participant will be seated at a 45 degree angle during this test.

The gastroduodenal tube will remain in place and the gastrointestinal manometry test will be performed again 4 hours later at the lunch meal. The lunch GDM measurements will be performed while sham or active TENS treatment is taking place.

[figure not shown]
[figure not shown]

Figure 4 shows the postprandial gastric motility following ingestion of a solid-liquid meal. Note the increased frequency of distal antral phasic contractions and coordination with pyloric and duodenal motility. Reproduced from ref. 11.

Figure 5 shows a correlation between distal antral contraction amplitude and rate of gastric emptying (12).

Analysis of manometric recordings

Antrum: Phasic pressure activity in the distal antrum recorded on the manometric tracing is quantified manually. The most distal antral site will be identified as a site recording up to three waves per minute, which is (a) just proximal (1cm) to a site recording duodenal-type wave or

(b) just proximal to a site exhibiting a mixture of antral-type and duodenal-type waves associated with baseline elevation (pyloric-type activity). For each sequential 15-minute period and for the 1-hour postcibal period, a motility index (MI) will be calculated using the formula: $MI = \log(\text{sum of amplitude} \times \text{number of contractions} + 1)$. The average 15-minute antral MI will be calculated, as previous studies showed that the cumulated slope of antral motility indices is linear (13).

Statistical Analysis

Sample size assessment - The standard deviation used for the sample size calculations was calculated from the observed value of distal antral activity in healthy volunteers in the absence of any treatment: 14.3 ± 0.66 (SD) (10,13). Comparison of 8 Participants in the active vs. sham treatment arms will have sufficient power to detect a difference between the 2 groups (Unpaired t-test; Parallel group design) of distal antral MI of 0.995 units or 7.0% relative to controls (10,13). It is to be noted that the antral MI measurement is on a logarithmic scale and, therefore, a 10% reduction in **antral** motility index is clinically relevant since it is associated with reduction in gastric emptying rate.

Response	Mean	SD	Predicted detectable effect size (%(absolute #)), n=8 per group unpaired analysis
Postprandial distal antral motility index	14.3	0.66	7.0% (0.995 MI units)

Data obtained from ref. 10; predicted detectable effect size is shown with 80% power, $\alpha=0.05$.

Statistical Methods

It is anticipated that the primary endpoint (the logarithmically transformed antral MI) will be normally distributed. We shall use an unpaired student's t-test to compare the antral MI in the sham versus active treatment groups.

An interim analysis will be performed for **“futility” assessment** after the first 8 participants. In such an analysis, we would have 4 patients per group, assessed in unpaired t test based on parallel group design. Using the same SD of 0.66, a comparison of 4 patients per group would have sufficient power to detect a significant difference in antral motility index of 1.572 (11 %). If the interim analysis shows that the antral MI difference between the 2 groups is <0.75 ($\sim 5\%$), we would consider whether it would be futile to continue the study and completing 16 participants. On the other hand, if the difference in mean antral MI is >0.75 in the two groups, we would complete the study. Since this interim analysis is conducted for “futility” rather than for efficacy, we will **not** correct the α statistic from 0.05 (e.g. to 0.025) on completion of the pre-specified sample of 16 subjects.

Anticipated Results and Significance

We anticipate a lower antral motility index with active T6 dermatomal TENS treatment compared to sham treatment. This physiological study will provide information about the potential effect of T6 dermatomal stimulation on gastroduodenal motility, that could play a role in inducing other effects currently under investigation (appetite reduction, gastric emptying etc).

Device Safety: Designation of Non-Significant Risk

Based on the FDA guidance on Significant Risk and Nonsignificant Risk Medical Device Studies (14), the proposed study does not meet the definition for a significant risk (SR) device study and hence is a non-significant risk (NSR) clinical study.

Moreover, the Elira TENS device is regarded as an NSR device on the following basis:

- It is not implantable
- It does not support or sustain human life
- It is not for use of substantial importance in diagnosing, curing, mitigating or treating a disease (no claims related to obesity have been made by the manufacturer)
- It does not present a potential for serious risk to the health, safety or welfare of the participant

It is important to note that the Elira TENS device is essentially similar to commercially-available, over-the-counter TENS units that can be purchased at local pharmacies and are commonly utilized for self-administered therapy.

Appendix 1

Test meal nutritional information:

Item	Amount	Unit	Weight (g)	Kcal	g Carbohydrate	g Protein	g Fat
Egg, Extra Large	2	Item	112	160	2	14	10
Bread, Whole Wheat	1	Slice	36	100	17	5	2
Jell-O® Vanilla Pudding	1	Item	110	110	23	1	1.5
Milk- 2%	1	Item	240	130	12	8	5
TOTAL	N/A	N/A	498	500	54	28	18.5

REFERENCES

1. Chen J. Mechanisms of action of the implantable gastric stimulator for obesity. *Obes Surg* 2004;14(Suppl. 1):S28-S32
4. Wolff, H. The mechanism and significance of the cold pressor response. *Q J Med* 1951;20:261-273

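### Does the plan leave open which antral motility index enters the t-test and the 0.75 futility rule?

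*Combined protocol and SAP*

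**What the plan says.** Experimental Design describes manometry after each meal, "with the primary measurement being the antral motility index during the first postprandial hour". The arms differ only at lunch, so the comparison of arms concerns the hour after lunch.

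The section on analysis of manometric recordings defines the index: "For each sequential 15-minute period and for the 1-hour postcibal period, a motility index (MI) will be calculated using the formula", namely the log of (sum of amplitudes × number of contractions + 1). It then adds: "The average 15-minute antral MI will be calculated, as previous studies showed that the cumulated slope of antral motility indices is linear". It does not say what the average is for.

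The statistical sections use shorter labels:

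- The normality statement expects that "the primary endpoint (the logarithmically transformed antral MI) will be normally distributed".
- The t-test is used "to compare the antral MI in the sham versus active treatment groups".
- The futility rule begins "If the interim analysis shows that the antral MI difference between the 2 groups is" and gives 0.75 units (about 5%) as the cut-off.
- The planning value of 14.3 (SD 0.66) was "calculated from the observed value of distal antral activity in healthy volunteers in the absence of any treatment", with no window attached.

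**The concern.** A reader who starts from Statistical Methods finds a test and an interim rule applied to an index that the document calculates in two ways. Nothing there says whether the one-hour value or the average of four 15-minute values is meant. The log base and amplitude unit are also missing.

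The two forms are not identical. The log of a total is not the average of the logs, and a quarter-hour without contractions scores log(0 + 1) = 0. That pulls the average down much further than the one-hour value. With 8 per arm at the end and 4 per arm at the interim, one unusual participant carries weight. If the form really were open, it could be chosen after the tracings had been read, and the choice could move a result across 0.05 or across 0.75.

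**Working it through.** **The plan's own figures.** Inputs from the sample size section and Statistical Methods: SD 0.66, 80% power, α = 0.05, unpaired t-test. The noncentral t calculation, two-sided, gives:

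- 8 per arm: 1.5066 × 0.66 = 0.994 (plan: 0.995; power at 0.995 is 80.0%).
- 4 per arm: 2.3808 × 0.66 = 1.571 (plan: 1.572; power at 1.572 is 80.0%).

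The power arithmetic is sound for whichever form has SD 0.66.

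**Even activity.** With n waves of equal amplitude A in each quarter, the quarter's product is An² and the hour's product is A(4n)² = 16An². The forms differ by ln 16 = 2.77 under a natural log. A constant cancels in a group difference, so the t-test is the same.

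**One silent quarter.** Assume a natural log, 14.3 as the one-hour mean, and the other quarters equal. The 15-minute index is then 14.3 − 2.773 = 11.527.

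- The average falls by 11.527/4 = 2.882.
- The one-hour MI falls by −2 ln(0.75) = 0.575.
- In an arm of 4 the mean moves by 2.882/4 = 0.720 against 0.575/4 = 0.144, a gap of 0.58.
- The two forms then fall on opposite sides of 0.75 only if the one-hour difference lies between 0.75 and 1.33 (silent quarter under sham) or between 0.17 and 0.75 (under active).

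**A sparse quarter.** Assume constant amplitude and 30 waves in each other quarter (the documents give no figure). With w waves in the sparse quarter, the average changes by 2 ln(w/30)/4 and the one-hour MI by 2 ln((90 + w)/120). For w = 3 these are −1.151 and −0.510.

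| Waves in the quarter | Change in average | Change in one-hour MI | Gap, arm of 4 |
|---|---|---|---|
| 0 | −2.882 | −0.575 | 0.58 |
| 1 | −1.70 | −0.55 | 0.29 |
| 3 | −1.151 | −0.510 | 0.16 |
| 10 | −0.549 | −0.365 | 0.05 |

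**Final test.** Take 8 normal scores per arm scaled to SD 0.66, with a difference of 0.995 (t = 3.015, p = 0.0093 before any change). Put the affected quarter in each sham participant in turn:

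| Waves | p, one-hour MI | p, 15-minute average |
|---|---|---|
| 0 | 0.009 to 0.025 | 0.14 to 0.25 |
| 3 | 0.009 to 0.022 | 0.012 to 0.059 |
| 10 | 0.009 to 0.017 | 0.009 to 0.024 |

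With a silent quarter in an active participant, both forms stay below 0.05 in every placement (largest p 0.012 for the one-hour MI, 0.030 for the average).

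**Log base and unit.** A change of unit multiplies every amplitude by the same factor. That adds a near-constant to every MI, which cancels. A change of base rescales the difference and the SD together and leaves t unchanged. The 0.75 cut-off does need the same base as 14.3 ± 0.66. At the ceiling of three waves per minute, a natural log turns 14.3 into a mean amplitude of (e^14.3 − 1)/180² ≈ 50 over one hour, or (e^14.3 − 1)/45² ≈ 802 over 15 minutes. If the unit is mmHg (an assumption), the first is the plausible reading, which points to a one-hour figure. Base 10 would need about 6 billion over the hour and can be ruled out. Base 2 gives 0.6 over the hour against 10.0 over 15 minutes and would reverse the inference, so this check is supportive only.

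**The case for a change.** The best case for a change is that Experimental Design fixes the window but not the summary. Four 15-minute indices averaged over the same hour also fit its words, and the manometry section goes out of its way to justify that average. The hypothesis is inhibition, so quiet spells are a plausible form of the effect. A quarter need not be silent for the forms to disagree: an 80% fall in contractions confined to one quarter throughout the active arm gives −2 ln(0.2)/4 = 0.80 on the average and −2 ln(3.2/4) = 0.45 on the one-hour MI, on either side of 0.75. Tracings are read by hand, and both forms are available from every one.

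Part of this stands: the role of the average is unstated, and Statistical Methods does not repeat the window. The rest carries less weight. "the primary measurement being the antral motility index during the first postprandial hour" most naturally means the MI that the manometry section defines for the one-hour period, and nothing in the document lets the shorter label in Statistical Methods override it. The reason given for the average, a linear cumulated slope, amounts to even activity over the hour, and that is the case in which the forms agree. Active stimulation runs for the full 60 minutes after the meal, so an effect confined to one quarter is not what the exposure suggests. The loss of significance in the final test needs a silent or nearly silent quarter in an unstimulated healthy volunteer who has just eaten.

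**Conclusion.** The concern does not call for a change. The plan names its primary measurement once, defines it by formula, and later refers to it by a shorter label. An analyst who follows Experimental Design runs a sound test. The missing cross-reference is a gap that analysts fill sensibly.

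The possible effect runs from nothing (even activity), through 0.05 units at the interim (10 waves instead of 30), to 0.58 units (one wholly silent quarter in one of 4 participants). These figures assume a natural log, 14.3 as a one-hour mean and equal activity in the other quarters. The documents give no rate of silent or sparse quarters, so they are conditional illustrations and not expected frequencies. The interim consequence is mild in any case: a difference below 0.75 commits the team only to considering whether to go on.

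Which window 14.3 ± 0.66 describes would have to be read from the cited sources. The plan's power figures hold for whichever form has that SD. A sentence in Statistical Methods pointing back to Experimental Design would be harmless, but it would alter neither the endpoint, the test nor the sample size.

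### The 80% power at 0.995 MI units leaves out the futility look at 4 per group; with the look, power lies between 64% and 80%

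*Combined protocol and SAP*

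**What the plan says.** Both parts are in the Statistical Analysis section of the combined protocol and SAP.

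- **Sample size assessment.** The SD of 0.66 (mean 14.3) comes from earlier data: "The standard deviation used for the sample size calculations was calculated from the observed value of distal antral activity in healthy volunteers". With 8 per group and an unpaired t-test, the detectable difference is 0.995 MI units, or 7.0%. The table note confirms the basis: "predicted detectable effect size is shown with 80% power", at alpha 0.05. The text adds that a 10% reduction in the antral "motility index is clinically relevant since it is associated with reduction in gastric emptying rate".
- **Statistical Methods.** A futility analysis follows the first 8 participants, 4 per group. The plan gives 1.572 units (11%) as the difference detectable at that point. The rule reads: "If the interim analysis shows that the antral MI difference between the 2 groups is <0.75" (about 5%), "we would consider whether it would be futile to continue the study and completing 16 participants". Above 0.75, the study is completed. Because the look is for futility and not efficacy, the plan will not correct the "α statistic from 0.05 (e.g. to 0.025) on completion of the pre-specified sample of 16 subjects".

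Neither part gives the power of the study with the look included.

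**The concern.** A look that can only end a study for futility does not inflate the type I error, so leaving alpha at 0.05 is not a fault. What such a look can do is lower power, because some trials that would have been significant at full size end early. The plan discusses alpha, which needs no correction, and is silent on power, which may change.

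The cut-off is also close to the headline effect. It lies 0.995 − 0.75 = 0.245 units below it, about half a standard error of the interim difference. A true effect of the size the plan says it can detect would often be flagged. A reader who takes 0.995 at 80% as the sensitivity of this design would be relying on a figure that holds only if the look is never acted on, and could read too much into a study that ended at 8 participants.

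**Working it through.** **Inputs from the plan.** SD 0.66; mean 14.3; alpha 0.05; 8 per group at the end; 4 per group at the look; cut-off 0.75; headline difference 0.995. The 10% effect is 0.10 × 14.3 = 1.43 units. Differences are signed so that a positive value means lower MI on active stimulation. Withdrawals are replaced, so 16 completers are taken.

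**Step 1: reproduce the plan's figures.** Power of a two-sample t-test from the noncentral t distribution with 2n − 2 degrees of freedom and noncentrality δ / (SD × √(2/n)), two-sided 0.05:
- n = 8 per group, δ = 0.995: power 80.05%; detectable difference at 80% is 0.994.
- n = 4 per group, δ = 1.572: power 80.03%; detectable difference 1.571.

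Both stated figures reproduce. The plan does not state sidedness. At n = 8, a one-sided test would give 0.863 and a two-sided normal approximation 0.925, so the plan's figures are two-sided t-test, fixed-sample figures with no allowance for the look.

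**Step 2: how often the look flags the study.** The SE of the interim difference is 0.66 × √(2/4) = 0.467. The probability of an interim difference below 0.75 is Φ((0.75 − δ)/0.467):
- δ = 0.995: Φ(−0.525) = 30.0%.
- δ = 1.43: Φ(−1.457) = 7.3%.

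**Step 3: power with the look.** Simulation of 4,000,000 trials per scenario, with the first 4 per group nested in the 8 and the final t-test on 14 degrees of freedom. In the always-stop case, a flagged trial counts as not significant.

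| True difference | Flagged | Always stop | Never stop | Largest loss |
|---|---|---|---|---|
| 0.995 (7.0%) | 30.0% | 63.6% | 80.0% | 16 points |
| 1.43 (10%) | 7.3% | 91.9% | 98.0% | 6 points |

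Applying the cut-off to the absolute difference leaves these powers unchanged.

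**Step 4: what is lost among flagged trials.** The share that would have been significant at 16 is the loss divided by the flagged proportion:
- δ = 0.995: (0.8000 − 0.6360)/0.3001, about 55%.
- δ = 1.43: (0.9805 − 0.9189)/0.0727, about 85%, of far fewer flagged trials.

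**Step 5: detectable difference if the cut-off is always followed.** Simulated power reaches 80.0% at 1.195 units; 1.195/14.3 = 8.4%, compared with the stated 7.0%.

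**Step 6: sensitivity to the SD.** The 0.66 comes from cited studies. An SD 20% lower (0.528) or higher (0.792) is an assumption; 1,000,000 trials each.

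| SD | Power at 0.995, always to never stop | Power at 1.43, always to never stop | Always-stop detectable difference |
|---|---|---|---|
| 0.528 | 73.0% to 93.8% | 96.5% to 99.9% | 1.08 |
| 0.66 | 63.6% to 80.0% | 91.9% to 98.0% | about 1.2 |
| 0.792 | 53.5% to 64.7% | 84.8% to 91.8% | 1.34 |

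The largest loss due to the look itself is 21, 16 and 11 points at 0.995, and 3, 6 and 7 points at 1.43, in the order of the rows.

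**The case against.** The strongest reply has four parts.

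- **The 80% is labelled as an analysis of 8 per group and is right for that.** True. But the look is part of the same plan, and no other power figure is given for the study as designed.
- **The rule is discretionary, so 64% needs automatic stopping that the plan does not prescribe.** This stands, and it is why the result is a range. The loss shrinks with the share of flagged trials that are stopped. If half were stopped, chosen independently of the data (an illustrative assumption), power would be (63.6 + 80.0)/2 = 72% at 0.995 and (91.9 + 98.0)/2 = 95% at 1.43. Discretion reduces the loss; it does not remove it.
- **The effect that matters is 10%, where power is at least 92% at the plan's SD.** This also stands, and it limits the consequence. The figure the plan reports in both text and table is nevertheless 0.995 at 80%.
- **In a 16-person physiological study, giving up some power for the chance to end at 8 is legitimate.** Agreed. The trade-off is acceptable, but the plan should state its price.

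A smaller point concerns counting every stopped trial as non-significant. About 4% of flagged trials at 0.995 have an interim p-value below 0.05. Counting them as successes raises the lower bound only to 64.8%.

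**Conclusion.** The concern holds. The stated 80% describes a study without the interim look, and the plan describes one with it. The restated ranges rest on the plan's SD of 0.66, normally distributed MI, a two-sided test and 16 completers when the study continues. Their lower ends assume that every flagged trial stops, and their upper ends that none does. No single value between can be derived, because the plan does not say how the discretion would be used. This is an incomplete power statement that should be corrected. It is not a case against the sample size for a 10% effect, the alpha handling or the final test.

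**What to change.** In the Statistical Analysis section, do one of the following.

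- **Restate the power with the look included**, at SD 0.66: 64% to 80% at 0.995 units and 92% to 98% at 1.43 units, saying that the lower figures assume the study always stops below 0.75. Equivalently, give an 80%-power detectable difference of about 1.2 units (8.4%) if the cut-off is always followed. This costs one or two sentences and changes nothing in enrolment, procedures, cut-off or final test.
- **State that the look will not stop the study.** The 80% at 0.995 then stands as written. The cost is the chance to end at 8 participants when there is no effect.

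A lower cut-off is optional. It would reduce false stops but also reduce early stopping when there is no effect, and that balance is for the sponsor to choose.
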